11. MEASUREMENT OF EFFECT

11.1 Antitumor Effect

11.1.1 Definitions

Evaluable for toxicity. All patients will be evaluable for toxicity from the time of their first treatment with MLN0128 (TAK-228).

Evaluable for objective response. All patients who have measurable disease present at baseline, have begun treatment, and have had their disease re-evaluated will be considered evaluable for response. These patients will have their response classified according to the definitions stated below. (Note: Patients who exhibit objective disease progression prior to the end of cycle 1 will also be considered evaluable.)

11.1.2 Response Criteria

11.1.2.1 Evaluation

Complete hematologic response (CR)

Less than 5% blasts in a non-hypocellular marrow with a granulocyte count of $1 \times 10^9/L$ (or above), and a platelet count of $100 \times 10^9/L$ (or higher) and absence of peripheral blood blasts with complete resolution of any extra medullary disease. The patient is in sustained CR if they have previously achieved a CR and continue to meet the CR criteria (at least 28 days).

CR incomplete (CRi)
is called if patient meets all CR criteria except for residual neutropenia ($ANC < 1 \times 10^9/L$) or thrombocytopenia (platelets $< 100 \times 10^9/L$)

Partial Response (PR):
The presence of trilineage hematopoiesis in the bone marrow with recovery of ANC and platelet count to above levels, but with 5-25% bone marrow blasts and $\geq 50\%$ decrease in bone marrow blast percentage from baseline.

Morphologic leukemia-free state (MLFS)
If bone marrow blasts $< 5\%$, absence of Auer rods blasts, absence of extra medullary disease without hematological recovery.

No response (NR):
Failure to achieve CR/CRi/PR/MLFS after 2 cycles of MLN0128 (TAK-228).

Disease Progression:
At least a 25% increase in the absolute number of circulating blasts in peripheral blood, or at least 25% increase in bone marrow blasts, or development of extramedullary disease.

Relapse
Disease recurrence after achieving CR. Disease recurrence is defined by blast $\geq 5\%$ in the bone marrow, or recurrence of peripheral blood $> 5\%$ or extramedullary involvement.

11.1.3 Duration of Response

Duration of response is the duration of CR or CRi is measured from the time measurement criteria are first met for CR until the first date that recurrence is objectively documented.

12. DATA REPORTING / REGULATORY REQUIREMENTS

Adverse event lists, guidelines, and instructions for AE reporting can be found in Section 7.0 (Adverse Events: List and Reporting Requirements).

12.1 Study Oversight

This protocol is monitored at several levels, as described in this section. The Protocol Principal Investigator is responsible for monitoring the conduct and progress of the clinical trial, including the ongoing review of accrual, patient-specific clinical and laboratory data, and routine and serious adverse events; reporting of expedited adverse events; and accumulation of reported adverse events from other trials testing the same drug(s). The Protocol Principal Investigator and statistician have access to the data at all times through the CTMS web-based reporting portal.

The Protocol Principal Investigator will have conference calls with the Study Investigators to review accrual, progress, and pharmacovigilance every two months for the first year that the study is accruing patients and then every three months after the first year. Decisions to proceed to the second stage of a Phase 2 trial will require sign-off by the Protocol Principal Investigator and the Protocol Statistician through IWRS and Medidata Rave.

All Study Investigators at participating sites who register/enroll patients on a given protocol are responsible for timely submission of data via Medidata Rave and timely reporting of adverse events for that particular study. This includes timely review of data collected on the electronic CRFs submitted via Medidata Rave.

All studies are also reviewed in accordance with the enrolling institution's data safety monitoring plan.

12.2 Data Reporting

Data collection for this study will be done exclusively through Medidata Rave. Access to the trial in Rave is granted through the iMedidata application to all persons with the appropriate roles assigned in the Regulatory Support System (RSS). To access Rave via iMedidata, the site user must have an active CTEP IAM account (<https://eapps-ctep.nci.nih.gov/iam>) and the appropriate Rave role (Rave CRA, Read-Only, or Site Investigator) on either the lead protocol organization or participating organization roster at the enrolling site.

Upon initial site registration approval for the study in RSS, all persons with Rave roles assigned on the appropriate roster will be sent a study invitation e-mail from iMedidata. To accept the invitation, site users must log into the Select Login (<https://login.imedidata.com/selectlogin>) using their CTEP-IAM user name and password, and click on the "accept" link in the upper right-corner of the iMedidata page. Please note, site users will not be able to access the study in Rave until all required Medidata and study specific trainings are completed. Trainings will be in the form of electronic learnings (eLearnings), and can be accessed by clicking on the link in the upper right pane of the iMedidata screen.

Users that have not previously activated their iMedidata/Rave account at the time of initial site registration approval for the study in RSS will also receive a separate invitation from iMedidata to activate their account. Account activation instructions are located on the CTSU website, Rave tab under the Rave resource materials (Medidata Account Activation and Study Invitation Acceptance). Additional information on iMedidata/Rave is available on the CTSU website under the Rave tab at www.ctsu.org/RAVE/ or by contacting the CTSU Help Desk at [name] or by e-mail at [contact].

12.2.1 Method

This study will be monitored by the Clinical Trials Monitoring Service (CTMS). Data will be submitted to CTMS at least once every two weeks via Medidata Rave (or other modality if approved by CTEP). Information on CTMS reporting is available at: <http://www.theradex.com/CTMS>. On-site audits will be conducted on an 18-36 month basis as part of routine cancer center site visits. More frequent audits may be conducted if warranted by accrual or due to concerns regarding data quality or timely submission. For CTMS monitored studies, after users have activated their accounts, please contact the Theradex Help Desk at [contact] or by email at [contact] for additional support with Rave and completion of CRFs.

12.2.2 Responsibility for Data Submission

For ETCTN trials, it is the responsibility of the PI(s) at the site to ensure that all investigators at the ETCTN Sites understand the procedures for data submission for each ETCTN protocol and that protocol specified data are submitted accurately and in a timely manner to the CTMS via the electronic data capture system, Medidata Rave.

Data are to be submitted via Medidata Rave to CTMS on a real-time basis, but no less than once every 2 weeks. The timeliness of data submissions and timeliness in resolving data queries will be tracked by CTMS. Metrics for timeliness will be followed and assessed on a quarterly basis. For the purpose of Institutional Performance Monitoring, data will be considered delinquent if it is greater than 4 weeks past due.

Data from Medidata Rave and CTEP-AERS is reviewed by the CTMS on an ongoing basis as data is received. Queries will be issued by CTMS directly within Rave. The queries will appear on the Task Summary Tab within Rave for the CRA at the ETCTN to resolve. Monthly web-based reports are posted for review by the Drug Monitors in the IDB, CTEP. Onsite audits will be conducted by the CTMS to ensure compliance with regulatory requirements, GCP, and NCI policies and procedures with the overarching goal of ensuring the integrity of data generated from NCI-sponsored clinical trials, as described in the ETCTN Program Guidelines, which may be found on the CTEP (http://ctep.cancer.gov/protocolDevelopment/electronic_applications/adverse_events.htm) and CTSU websites.

An End of Study CRF is to be completed by the PI, and is to include the recommended phase 2 dose (RP2D), and a description of any dose-limiting toxicities (DLTs). CTMS will utilize a core set of eCRFs that are Cancer Data Standards Registry and Repository (caDSR) compliant (<http://cbiit.nci.nih.gov/ncip/biomedical-informatics-resources/interoperability-and-semantics/metadata-and-models>). Customized eCRFs will be included when appropriate to meet unique study requirements. The PI is encouraged to review the eCRFs, working closely with CTMS to ensure prospectively that all required items are appropriately captured in the eCRFs prior to study activation. CTMS

will prepare the eCRFs with built-in edit checks to the extent possible to promote data integrity.

CDUS data submissions for ETCTN trials activated after March 1, 2014, will be carried out by the CTMS contractor, Theradex. CDUS submissions are performed by Theradex on a monthly basis. The trial's lead institution is responsible for timely submission to CTMS via Rave, as above.

Further information on data submission procedures can be found in the ETCTN Program Guidelines (http://ctep.cancer.gov/protocolDevelopment/electronic_applications/adverse_events.htm).

12.3 Collaborative Agreements Language

The agent(s) supplied by CTEP, DCTD, NCI used in this protocol is/are provided to the NCI under a Collaborative Agreement (CRADA, CTA, CSA) between the Pharmaceutical Company(ies) (hereinafter referred to as "Collaborator(s)") and the NCI Division of Cancer Treatment and Diagnosis. Therefore, the following obligations/guidelines, in addition to the provisions in the "Intellectual Property Option to Collaborator" (http://ctep.cancer.gov/industryCollaborations2/intellectual_property.htm) contained within the terms of award, apply to the use of the Agent(s) in this study:

1. Agent(s) may not be used for any purpose outside the scope of this protocol, nor can Agent(s) be transferred or licensed to any party not participating in the clinical study. Collaborator(s) data for Agent(s) are confidential and proprietary to Collaborator(s) and shall be maintained as such by the investigators. The protocol documents for studies utilizing Agents contain confidential information and should not be shared or distributed without the permission of the NCI. If a copy of this protocol is requested by a patient or patient's family member participating on the study, the individual should sign a confidentiality agreement. A suitable model agreement can be downloaded from: <http://ctep.cancer.gov>.
2. For a clinical protocol where there is an investigational Agent used in combination with (an)other Agent(s), each the subject of different Collaborative Agreements, the access to and use of data by each Collaborator shall be as follows (data pertaining to such combination use shall hereinafter be referred to as "Multi-Party Data"):
 - a. NCI will provide all Collaborators with prior written notice regarding the existence and nature of any agreements governing their collaboration with NCI, the design of the proposed combination protocol, and the existence of any obligations that would tend to restrict NCI's participation in the proposed combination protocol.
 - b. Each Collaborator shall agree to permit use of the Multi-Party Data from the clinical trial by any other Collaborator solely to the extent necessary to allow said other Collaborator to develop, obtain regulatory approval or commercialize its own Agent.

- c. Any Collaborator having the right to use the Multi-Party Data from these trials must agree in writing prior to the commencement of the trials that it will use the Multi-Party Data solely for development, regulatory approval, and commercialization of its own Agent.
- 3. Clinical Trial Data and Results and Raw Data developed under a Collaborative Agreement will be made available to Collaborator(s), the NCI, and the FDA, as appropriate and unless additional disclosure is required by law or court order as described in the IP Option to Collaborator (http://ctep.cancer.gov/industryCollaborations2/intellectual_property.htm). Additionally, all Clinical Data and Results and Raw Data will be collected, used and disclosed consistent with all applicable federal statutes and regulations for the protection of human subjects, including, if applicable, the *Standards for Privacy of Individually Identifiable Health Information* set forth in 45 C.F.R. Part 164.
- 4. When a Collaborator wishes to initiate a data request, the request should first be sent to the NCI, who will then notify the appropriate investigators (Group Chair for Cooperative Group studies, or PI for other studies) of Collaborator's wish to contact them.
- 5. Any data provided to Collaborator(s) for Phase 3 studies must be in accordance with the guidelines and policies of the responsible Data Monitoring Committee (DMC), if there is a DMC for this clinical trial.
- 6. Any manuscripts reporting the results of this clinical trial must be provided to CTEP by the Group office for Cooperative Group studies or by the principal investigator for non-Cooperative Group studies for immediate delivery to Collaborator(s) for advisory review and comment prior to submission for publication. Collaborator(s) will have 30 days from the date of receipt for review. Collaborator shall have the right to request that publication be delayed for up to an additional 30 days in order to ensure that Collaborator's confidential and proprietary data, in addition to Collaborator(s)'s intellectual property rights, are protected. Copies of abstracts must be provided to CTEP for forwarding to Collaborator(s) for courtesy review as soon as possible and preferably at least three (3) days prior to submission, but in any case, prior to presentation at the meeting or publication in the proceedings. Press releases and other media presentations must also be forwarded to CTEP prior to release. Copies of any manuscript, abstract and/or press release/ media presentation should be sent to email: [contact]

The Regulatory Affairs Branch will then distribute them to Collaborator(s). No publication, manuscript or other form of public disclosure shall contain any of Collaborator's confidential/ proprietary information.

13. STATISTICAL CONSIDERATIONS

13.1 Study Design/Endpoints

This is a phase II study in relapsed or refractory ALL patients treated with MLN0128 (TAK-228). This study will use a one-stage design with an interim analysis to evaluate the efficacy of MLN0128 (TAK-228) in this patient population.

13.1.1 Primary Endpoint

The primary endpoint of this trial is complete response (CR, CRi) rate. A complete response will be considered synonymous with “success”. All patients meeting the eligibility criteria who have signed a consent form and have begun treatment will be evaluable for response.

13.1.2 Primary Analyses Plan

The interim and final analyses for this trial will commence at the time the patients have become evaluable for the primary endpoint. Analyses at other time points will be a decision made by the Statistician and Study Chair, in accord with CCS Standard Operating Procedures, availability of data for secondary endpoints, and the level of data maturity. It is anticipated that the earliest date in which the results will be made available via manuscript, abstract, or presentation format is when the last patient registered has been followed for at least 6 months.

13.1.2.1 Definition of Primary Endpoint

The primary endpoint of this trial is complete response rate. A complete response is defined to be a CR or CRi noted as the objective status at any time during treatment. Response will be evaluated using all cycles of treatment. All patients meeting the eligibility criteria who have signed a consent form and have begun treatment will be evaluable for response.

13.1.2.2 Estimation

The proportion of successes will be estimated by the number of successes divided by the total number of evaluable patients. Ninety-five percent Duffy-Santner confidence intervals for the true success proportion will be calculated.

13.1.2.3 Primary Endpoint Evaluable Patient Exception

Patients not being treated at the safe dose level (see section 13.5) will be summarized separately for the primary endpoint and will not be included when evaluating the final decision rule.

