13.1.2.4 Decision Rule

Previous studies in relapsed or refractory ALL have shown a CR rate ranging from 20 to 47% (61, 62). Responses can vary by factors such as first or second relapse and age. Due to the heterogeneity of this disease, a response rate of 10% with MLN0128 (TAK-228) would not be of interest. The largest success proportion where the proposed treatment regimen would be considered ineffective in this population is 10%, and the

smallest success proportion that would warrant subsequent studies with the proposed regimen in this patient population is 30%. The following one-stage design with an interim analysis uses 26 evaluable patients to test the null hypothesis that the true success proportion in a given patient population is at most 10%.

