13.1.2.5 Interim Analysis

Enter 11 evaluable patients into the study. If 1 or fewer successes are observed in the first 11 evaluable patients, we will consider this regimen ineffective in this patient population and terminate this study. Otherwise, if the number of successes is at least 2, we will continue accrual.

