13.1.2.6 Final Decision Rule

Enter 26 evaluable patients into the study. If 4 or fewer successes are observed in the first 26 evaluable patients, we will consider this regimen ineffective in this patient population. If 5 or more successes are observed in the first 26 evaluable patients, we may recommend further testing of this regimen in subsequent studies in this population.

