13.1.3 Power and Significance Level

Assuming that the number of successes is binomially distributed, the significance level is .09, i.e. there is a 9% chance of finding the drug to be effective when it truly is not. The probability of declaring that this regimen warrants further study (i.e. statistical power) and the probability of stopping at the interim analysis under various success proportions can be tabulated as a function of the true success proportion as shown in the following table.

If the true success proportion is...	0.10	0.15	0.20	0.25	0.30
Then the probability of declaring that the regimen warrants further study is...	0.09	0.28	0.52	0.72	0.85
and the probability of stopping at the interim analysis is ...	0.70	0.49	0.32	0.20	0.11

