13.5 Safety Analysis

13.5.1 A safety analysis will be performed after the first 6 patients have been accrued to the study on dose 0 (3 mg, orally days 1-21). If 2 or more of the first 6 patients experience a dose-limiting toxicity (DLT) as defined below, then 6 patients will be enrolled on dose -1 (2 mg, orally days 1-21). If 2 or more of the second 6 patients experience DLT, then the study will be terminated.

13.5.2 Toxicity will be measured per NCI-CTCAE version 4. DLT is defined as an adverse event possibly, probably, or definitely related to study treatment that meets one of the following:

- Any grade 4 drug-related non-hematological toxicity
- Any grade 3 drug-related non-hematological toxicity that does not resolve to < grade 3 within 3 days, with the following exceptions:
 - Grade 3 Bilirubin, AST, ALT, Alkaline phosphatase will be considered DLT only if it does not recover to <grade 3 within 7 days
- Myelosuppression: hypoplasia (bone marrow cellularity <10%) >50 days

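### After a dose de-escalation, patients at the abandoned dose leave the final rule but, as written, stay in the interim futility rule, so the operating characteristics in 13.1.3 no longer apply

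*Combined protocol and SAP*

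**What the plan says.** Section 13.1.2.1 makes every eligible, consented patient who has begun treatment evaluable for response, whatever the dose. Section 13.1.2.3 then makes one exception: patients not at the safe dose are summarized separately for the primary endpoint and "will not be included when evaluating the final decision rule".

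The interim rule in 13.1.2.5 stops the study "If 1 or fewer successes are observed in the first 11 evaluable patients". It names no dose. The final rule in 13.1.2.6 is positive "If 5 or more successes are observed in the first 26 evaluable patients".

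Section 13.5.1 looks at the first 6 patients at dose 0. If 2 or more have a DLT, "then 6 patients will be enrolled on dose -1". Section 13.2.1 allows for this with 6 extra patients: 26 + 6 + 3 = 35.

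Section 13.1.3 says that "the significance level is .09" and gives one table. At true rates of 10% and 30%, the probability of a positive result is 0.09 and 0.85, and the probability of stopping at the interim is 0.70 and 0.11.

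**The concern.** The two rules draw on different patients once the dose has been reduced. The 6 patients at the abandoned dose cannot contribute to a positive final result, yet read literally they make up more than half of the 11 who decide whether the study continues. For example, 0 of 6 at the abandoned dose and 1 of 5 at dose -1 is 1 success in 11, and the study ends.

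The table in 13.1.3 rests on the 11 interim patients being a subset of the final 26, with one common response rate. After de-escalation only 5 of the 11 belong to the 26, and the other 6 may have a different rate. The futility decision about the retained dose would then follow a rule whose error rates the plan does not give.

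**Working it through.** **Inputs.** From the plan: null rate 0.10 and target rate 0.30 (13.1.2.4); stop at 1 or fewer successes in 11 (13.1.2.5); positive at 5 or more in 26 (13.1.2.6); de-escalate at 2 or more DLTs in 6 (13.5.1). Assumed, because the documents do not give them: the DLT rate in this population, and the CR/CRi rate pa in the abandoned cohort.

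**1. The plan's own figures.** Write p for the true rate.

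- P(stop) = P(X ≤ 1), X ~ Bin(11, p)
- P(positive) = Σ over x = 2 to 11 of P(X = x) · P(Bin(15, p) ≥ 5 − x)

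| p | P(positive) | P(stop) |
|---|---|---|
| 0.10 | 0.0865 | 0.697 |
| 0.15 | 0.282 | 0.492 |
| 0.20 | 0.519 | 0.322 |
| 0.25 | 0.719 | 0.197 |
| 0.30 | 0.852 | 0.113 |

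All ten table entries agree after rounding. The table is therefore for the two-look design with nested patients and one rate.

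**2. The rules as written, after de-escalation.** Let A ~ Bin(6, pa) be successes at the abandoned dose and B ~ Bin(5, p) successes among the first 5 at dose -1. The final 26 are those 5 plus 21 more.

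- P(stop) = P(A + B ≤ 1)
- P(positive) = Σ over a + b ≥ 2 of P(A = a) · P(B = b) · P(Bin(21, p) ≥ 5 − b)

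*Equal rates.* At p = pa = 0.10, alpha is 0.058. At p = pa = 0.30, power is 0.831. P(stop) is unchanged at 0.697 and 0.113. Both probabilities of a positive result fall because the interim now shares only 5 patients with the final analysis, so passing it says less about the final count.

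*Unequal rates, p = 0.30 at dose -1:*

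| Abandoned cohort (assumed) | Power | P(stop) |
|---|---|---|
| 40% | 0.88 | 0.06 |
| 30% | 0.83 | 0.11 |
| 20% | 0.75 | 0.20 |
| 2 of 6 cannot respond, other 4 at 30% | 0.76 | 0.20 |
| 10% | 0.63 | 0.34 |

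The fourth row can be checked by hand for stopping: 4 + 5 = 9 patients at 30%, so P(X ≤ 1) = 0.7⁹ + 9(0.3)(0.7⁸) = 0.040 + 0.156 = 0.196.

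*Alpha, p = 0.10 at dose -1:* 0.058 at pa = 0.10, 0.079 at 0.20, 0.093 at 0.30. It cannot exceed 0.112, the value for 5 or more of 26 with no interim.

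**3. How often this arises.** P(2 or more DLTs in 6) = 1 − (1 − d)⁶ − 6d(1 − d)⁵. At d = 1/11 this is 1 − 0.564 − 0.339 = 0.097; at d = 0.20 it is 0.345; at d = 0.33 it is 0.642. The 1/11 is the count at 3 mg daily in Section 2.2.7, from a different study.

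**Limits.** The 6 + 5 split assumes that accrual moves to dose -1 directly after patient 6. The figures in step 2 also leave aside the second DLT check at dose -1, which can end the study on its own.

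**The case against.** **The exception may have been meant for both looks.** The heading of 13.1.2.3 speaks of an exception for evaluable patients, the section stands before both rules, and its first half sets these patients apart for the primary endpoint as a whole. Section 13.1.2.7 links the target at the safe dose with the stopping rule. This is a fair reading, and it may be what was intended. But no section says it for the interim, and the one rule that 13.1.2.3 names is the final one. A rule that ends the study should not depend on inference.

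**The scenario may be unlikely.** At a DLT rate of 1/11, power averaged over whether de-escalation occurs is 0.850, 0.842 or 0.830 for an abandoned-cohort rate of 30%, 20% or 10%, against 0.85 stated. That stands at this DLT rate. The chance of de-escalation rises to 0.34 or 0.64 at assumed rates of 0.20 or 0.33.

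**A lower response in the abandoned cohort is not established.** That dose is the higher one. Section 6 allows many patients with toxicity to resume one level lower, so some of the 6 may in fact receive dose -1. This stands too. A reader might infer that the study would stop on the wrong dose, or that power collapses to 0.46. The documents support neither. Power of 0.46 needs none of the 6 to be able to respond, and even 0.63 needs a 10% rate. The DLT trigger guarantees only that at least 2 of the 6 had a DLT; if exactly those 2 cannot respond, power is 0.76.

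**Pooling for early futility could be deliberate.** It is defensible as a way to limit exposure to an inactive drug. If so, the plan should say so and give the error rates that follow.

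**Conclusion.** The point holds on the text, within limits. As written, the exclusion reaches the final rule only. If de-escalation occurs, 6 of the 11 interim patients come from a dose that the final rule ignores, and the table in 13.1.3 does not apply. With equal response in the two cohorts the consequence is small and conservative for alpha: 0.058, with power 0.83. It becomes material if the abandoned cohort responds less often, with power about 0.75 and early stopping about 0.20 at an assumed 20%, and power 0.63 with early stopping 0.34 at 10%. It goes the other way if that cohort responds more often (0.88 and 0.06 at 40%). These unequal-rate figures rest on assumed response rates and on the 6 + 5 split. Without de-escalation the stated figures are right. The plan should be corrected because the correction is short and a binding stop depends on it. The point concerns only which patients enter the analysis and implies nothing about which dose is right.

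**What to change.** In 13.1.2.3, extend the exclusion so that it covers the interim as well as the final decision rule. In 13.1.2.5, define the 11 as the first 11 evaluable patients enrolled at the dose level retained under 13.5. The interim 11 are then again a subset of the final 26 at one dose, and the stated figures return: alpha 0.0865 (printed as 0.09), power 0.852, stopping 0.697 and 0.113.

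Maximum accrual stays at 6 + 26 + 3 = 35. The cost is timing. After de-escalation the futility look comes at about 6 + 11 = 17 treated patients instead of 11, roughly 6 months later at the 1 patient per month in 13.2.2. If the true rate is 10% at both doses, that is about 6 × 0.697 = 4.2 more patients treated on average before a stop, given de-escalation.

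If the sponsor prefers to pool both doses for early futility, 13.1.2.5 should say so and 13.1.3 should give a second table for the de-escalated case.
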